Liposomal bupivacaine (LB) is a long-acting local anesthetic that has been shown to promote local pain control in the postoperative period for up to 72 hours, as compared to traditional local anesthetic agents with half-lives ranging from 1-6 hours. The prolonged pain control duration is the result of suspending the bupivacaine within a lipid vessel that creates slow release of the medication within tissues over time. Within the realm of urology very few studies have assessed outcomes in patients who receive perioperative LB. A study by Cotta et al from 2016 retrospectively explored their experience with LB (n=13) compared with those receiving local bupivacaine (n=24) for anesthesia during penile prosthesis placement.[6] The authors found that patients receiving LB used significantly fewer opioids postoperatively. Two additional studies by Alom et al and [name] et al described LB for use with office-based surgical procedures involving the penis and scrotum, although outcomes related to pain control were not specifically evaluated.[7,8] Finally, a recent study by Taniguchi and Mulhall showed that LB did not adversely impact systemic hemodynamics when administered within the corpora cavernosa of patients at the time of penile prosthesis placement, supporting the safety of this medication in the perioperative setting.[9]

It has been our experience that LB optimizes pain control in the postoperative setting when administered at the time of penile prosthesis placement. This has become a routine part of clinical practice. However, LB results in added expense, and to date there has never been an adequately powered prospective study comparing outcomes between LB and other shorter-acting local anesthestics to determine if this added expense is justified. Therefore, we intend to assess perioperative and postoperative outcomes including safety and pain control in patients who receive local anesthesia with LB versus ropivacaine at the time of penile prosthesis placement.

References:

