Study participants will be randomized to one of two study arms. Arm 1 will receive 40 mL of ropivicaine to be used for local anesthetic infiltration. Arm 2 will receive 40 mL of Liposomal bupivacaine (20 mL Exparel + 10 mL 0.25% bupivacaine) to be used for local anesthetic infiltration. The patient will be blinded to which study arm he is randomized to, but the surgeon will be aware (i.e. single blind). The specific agent (determined by study randomization) will be ordered by the performing surgeon through the "prep for case" inflatable penile prosthesis order set within EPIC. Two standardized order sets will be shared amongst the three performing surgeons and will also include standardized perioperative medication administration per a previously published enhanced recovery protocol (see reference #5 – Lucas et al).

Local anesthetic will be administered via a standard protocol at the time of penile prosthesis surgery. The block itself will include pudendal, scrotal, dorsal penile, and inguinal nerve blocks. The remainder of the penile prosthesis surgery will be per standard practice, with all surgeons currently utilizing a similar penoscrotal

approach. Of note, patients who currently receive intraoperative LB routinely wear a disposable bracelet with information for medical professionals regarding the recent receipt of this medication. This is worn for 72-96 hours postoperatively. For the study protocol, we will work with the perioperative nursing team to apply a similar bracelet describing the research study and acknowledging that each patient may have received LB versus ropivacaine during the surgery.

If the study coordinator is unable to meet with the patient to review consent, they will be a digital consent via email. The patient will be contacted by telephone and read a script about study participation. Patients will then have the ability to sign the consent form with their personal device. These digital consent forms will be stored in Ptrax.

If patients decide to consent digitally, they will be asked to complete the baseline requirements over the phone. These documents are the baseline anxiety inventory and the pain catastrophizing scale which will be recorded by the study coordinator.

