Note: The Date Range must include the period for collection of baseline data, as well as follow-up data, if applicable.

The study involves data that exist at the time of IRB submission **and** data that will be generated after IRB submission. Include this activity in the Methods section. Examples

- The study plans to conduct a retrospective chart review and ask subjects to complete a questionnaire.
- The study plans to include subjects previously diagnosed with a specific disease and add newly diagnosed subjects in the future.

The study will use data that have been collected under another IRB protocol. Include in the Methods section and enter the IRB number from which the research material will be obtained. *When appropriate, note when subjects have provided consent for future use of their data and/or specimens as described in this protocol.*

Enter one IRB number per line, add more lines as needed

🗌 Data	Specimens Data & Specimens	
🗌 Data	Specimens Data & Specimens	
🗌 Data	Specimens Data & Specimens	

Data Analysis

Power analyses may not be appropriate if this is a feasibility or pilot study, but end-point analysis plans are always appropriate even if only exploratory. Provide all information requested below, or provide justification if not including all of the information.

Power Statement: A total sample size of 110 (55 per arm) provides 90% power to detect a clinically relevant difference in discharge prescription opioids of 37.5 OME, based on a two-sample, two-sided, equal-variance t-test with significance alpha level 0.05, and assuming a common standard deviation of 60 OME. With an anticipated drop-out rate of 18%, total sample size will be 130 (65 per arm).

Data Analysis Plan:

Patient data will be recorded and stored in a study-specific database through RedCap. This database will be created by the primary investigator. At the completion of the study, statistical analyst support will be used to perform the final data analysis.

Preoperative data collection:

-State-Trait Anxiety inventory (attachment 1) -Pain Catastrophizing scale (attachment 2)

Postoperative days 3,7,14 data collection:

-Visual-analogue pain score (attachment 3)

-Visual-analogue anxiety score (attachment 4)

-Analgesic quantities (acetaminophen, meloxicam, ibuprofen, gabapentin, oxycodone, tramadol)

Endpoints

Primary:

1. Postoperative opioid pain medication use (number of oral morphine equivalents consumed per day and total number)

Secondary:

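### The power statement is written for opioids prescribed at discharge while the primary endpoint is opioids consumed, and no available text says that discharge prescribing is set independently of the arm known to the surgeon

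*Combined protocol and SAP*

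**What the plan says.** All references are to the combined protocol and SAP.

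- **Data Analysis, Power Statement.** "A total sample size of 110 (55 per arm) provides 90% power", and the quantity named is opioids prescribed at discharge: "90% power to detect a clinically relevant difference in discharge prescription opioids of 37.5 OME". The calculation is "based on a two-sample, two-sided, equal-variance t-test with significance alpha level 0.05", "assuming a common standard deviation of 60 OME".
- **Data Analysis, Endpoints.** The single primary endpoint is postoperative opioid use, measured as OME consumed, both daily and in total. Prescribed OME is not listed as a primary or secondary endpoint.
- **Study Design and Methods, blinding.** "The patient will be blinded to which study arm he is randomized to, but the surgeon will be aware (i.e. single blind"). The performing surgeon orders the allocated local anesthetic through an order set.
- **Study Design and Methods, co-medication.** "Two standardized order sets will be shared amongst the three performing surgeons and will also include standardized perioperative medication administration", following a published enhanced recovery protocol. Discharge opioids and refills are not mentioned there.
- **Study Design and Methods, data sources.** The patient keeps a log of opioid intake to day 14, is contacted on days 3, 7 and 14, and is asked to bring medication bottles at three weeks.
- **Background.** The investigators state a favourable view of one agent: "It has been our experience that LB optimizes pain control in the postoperative setting".

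**The concern.** Two problems meet in one sentence of the plan.

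The first is definitional. A prescribed quantity is a prescriber's decision and a consumed quantity is a patient's behaviour. They need not share a mean difference or a standard deviation. Consumption under the stated aims also takes in any in-hospital use, which a discharge prescription does not. A sample size derived for one does not establish the power for the other.

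The second is a possible route for bias. Blinding the patient protects how he judges and reports his need for opioids. It does not blind whoever decides how much he has at home. If that person is the surgeon, who knows the arm and may expect LB patients to need less, supply could be lower in that arm. Where supply limits intake, consumed OME would fall with it, in the direction of the hypothesis, without any difference in pain relief. The plan does not call for prescribed OME by arm, so a reader of the results could not tell whether this had happened.

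**Working it through.** **Inputs, all from the Power Statement:** difference 37.5 OME, common SD 60 OME, two-sided alpha 0.05, equal-variance two-sample t-test, 55 per arm.

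**Step 1: reproduce the plan's figure.** The standardised difference is 37.5 / 60 = 0.625. Solving the noncentral t power equation for 90% gives n = 54.78, rounded up to 55 per arm. Power at 55 per arm is 90.1%. The stated figure reproduces, so the arithmetic is not at issue.

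**Step 2: compare the quantities.**

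| Place | Quantity | Difference and SD given? |
|---|---|---|
| Power Statement | OME prescribed at discharge | 37.5 and 60 |
| Endpoints, primary | OME consumed, daily and total | none |

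If 37.5 and 60 also hold for total consumption, 55 per arm stands unchanged. If they do not, the power changes. As an illustration, keep 37.5 and 55 per arm and assume another SD for consumption. SD 50 gives 37.5 / 50 = 0.75 and power of about 97%. SD 70 gives 37.5 / 70 = 0.536 and power of about 80%. The documents do not say which SD applies to consumption.

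**Step 3: what a prescribing-driven shift would do.** Let b be the arm difference in mean *consumed* OME produced by prescribing alone, with no analgesic difference. The documents give no value, so b is assumed.

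- Standard error of the difference: 60 × √(2/55) = 11.44 OME.
- Critical value of t on 108 degrees of freedom: 1.982. An observed difference of 1.982 × 11.44 = 22.7 OME reaches significance.
- Noncentrality: b / 11.44. The chance of a significant result is the area of the noncentral t beyond ±1.982.

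| Assumed b (OME consumed) | b / 37.5 | b / 11.44 | Chance of p < 0.05 |
|---|---|---|---|
| 0 | 0% | 0 | 5% |
| 5 | 13% | 0.44 | 7% |
| 7.5 | 20% | 0.66 | 10% |
| 15 | 40% | 1.31 | 26% |

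**Step 4: carry-over.** Prescribing changes consumption only for patients who would otherwise have used more than they were given. If a fraction c of a prescribing shift p carries over, b = c × p. For p = 15 OME, c = 1 gives b = 15 (26%), c = 1/2 gives b = 7.5 (10%), and c = 1/3 gives b = 5 (7%). If nearly all patients have tablets left over, c is near zero and so is the bias.

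**The case against.** The strongest case on the other side has five parts.

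- **Who prescribes.** A reader might infer that the surgeon controls the discharge opioid supply. No section says so. The Methods say only that the surgeon orders the local anesthetic. This objection stands, and the point is therefore conditional. The inference is not far-fetched, since the Background itself describes surgeons as major prescribers of postoperative opioids.
- **The endpoint is already consumption.** This stands. The plan names consumed OME as primary and has it logged by a blinded patient, with a request to bring the bottles at three weeks. Any effect of prescribing is indirect. What needs correcting is the Power Statement, not the choice of endpoint.
- **The power wording may be loose.** The phrase could mean discharge opioids that were taken. In that case SD 60 describes intake and says nothing about whether supply varies, so the SD cannot be used as evidence that supply is not fixed. This stands too. It is a reason to reconcile the two sections.
- **Standardization may already cover it.** The order sets and the perioperative analgesia attachment might fix discharge analgesia equally in both arms. They cannot be seen in full, so absence cannot be claimed. The description that is available mentions neither discharge opioids nor refills, and two order sets would allow one per arm.
- **Prior belief is modest.** The Background statement on LB is not a direct comparison with ropivacaine, and the protocol regards both agents as generally standard of care. This weakens the presumption of bias but does not remove the route.

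**Conclusion.** The point holds in a limited form. It is certain from the text that the Power Statement and the primary endpoint name different quantities, so the 90% power is not shown for the endpoint to be analysed. It is also certain that the surgeon is unblinded and that no available section makes discharge prescribing or refills independent of the arm.

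Whether prescribing will differ by arm is not known. Under the stated assumptions (no drug effect, SD 60, 55 per arm) the false-positive chance would rise from 5% to about 7%, 10% or 26% for shifts of 5, 7.5 or 15 OME in consumption. These are illustrations, not estimates.

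A reader might go further and conclude that a positive result could not be attributed to the drug. The documents do not support that: supply has to limit intake for the route to operate, nothing shows that it does, and pain scores from blinded patients would also inform the interpretation. The point is worth acting on because it touches the primary outcome, the direction would favour the hypothesis, and the remedy is cheap.

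**What to change.** 1. Restate the Power Statement for total OME consumed over the log period, and justify the 37.5 OME difference and the SD of 60 for that quantity. If they hold, 55 per arm is unchanged; if not, recalculate.
2. State how the discharge opioid order relates to allocation. Either have it entered before the allocation is opened to the surgeon, with its content left to the surgeon, or confirm that the standardized order sets already make it the same in both arms. In either case, log later changes and refills with date and reason.
3. Report OME prescribed and refilled by arm beside OME consumed, as a descriptive check on differential prescribing.

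The cost is protocol wording, a sequencing step before allocation is opened, a short log and one more descriptive table. No additional patients are needed unless the justification in item 1 changes the difference or the SD. Whether the existing order sets can carry the sequencing step is for the site to confirm. If they already fix the discharge order equally, one sentence saying so settles most of item 2 and leaves only later changes and refills. No dose or quantity is proposed here.

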Preoperative patient data including pertinent demographics as well as a baseline anxiety inventory and pain catastrophizing scale will be collected. They will also receive a medication log to track their narcotic intake until post-operative day 14. The patients will be followed-up by phone call or through electronic correspondence (RedCap) on post-operative days 3, 7, and 14. Participants in the study will be allowed to completed the questionnaires through RedCap with a +/- 2 day allowance on completion to avoid any study deviation. This follow-up will be obtained by the performing surgeons and/or the research office coordinator. At these planned follow-up intervals, patients will be evaluated using the Visual Analog Pain Scale (daily maximum and minimum) and visual analogue anxiety scale (daily maximum and minimum). In addition their pain control regimen (quantities of Tylenol, anti-inflammatories, and opioid pain medication) will be analyzed. Patients will be instructed to bring their medication bottles to their 3 week follow-up. Patient satisfaction with overall postoperative pain control will be measured based on subjective response. Finally, the duration of local anesthetic effect will be measured based on patient report.

Subject Information

Target accrual is the proposed total number of subjects to be included in this study at Mayo Clinic. A "Subject" may include medical records, images, or specimens generated at Mayo Clinic and/or received from external sources.

Target accrual: 130 patients (65 patients in each treatment arm) – this accounts for the necessary statistical power plus an anticipated approximately 20% dropout rate.

Subject population (children, adults, groups): Patients with medication-refractory erectile dysfunction undergoing penile prosthesis placement at Mayo Clinic in Rochester by Drs. [name], [name], and [name].

Inclusion Criteria:

- Men undergoing 3-piece inflatable penile prosthesis placement under general anesthesia at Mayo Clinic

 Rochester
- 2. \geq 18 years old

Exclusion Criteria:

- 1. History of opioid exposure within the preceding 90 days prior to surgery (based on patient-report, review of the electronic medical record, and NMP prescribing database review)
- 2. Current or prior history of alcohol or drug abuse (illicit or prescription)
- 3. History of chronic pain conditions (chronic musculoskeletal pain, fibromyalgia, central sensitization, chronic pelvic pain syndrome, etc.)

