- 4. History of cardiac arrhythmia or untreated severe cardiovascular disease
- 5. Uncontrolled hypertension
- 6. Hepatic insufficiency
- 7. Renal insufficiency (CKD stage IIIa or greater)
- 8. Current anti-platelet or anti-coagulation therapy with plans to continue at the time of prosthesis placement
- 9. Poorly controlled diabetes mellitus (defined as HgbA1c > 8.5 within 30 days of surgery)
- 10. Concurrent adjunctive operative procedures planned at the time of penile prosthesis placement (examples: male urethral sling, Peyronie's disease straightening with penile plication or incision/grafting)
- 11. Concurrent non-prosthetic surgery planned at the time of penile prosthesis placement (examples: circumcision, hernia repair, hydrocelectomy, etc.)
- 12. Planned infrapubic or subcoronal incision at the time of penile prosthesis placement
- 13. Patients who will be undergoing prosthesis placement using local, monitored, or spinal anesthesia (i.e. non-general anesthesia)
- 14. Allergy or history of intolerance to any local anesthetic agents included in the protocol
- 15. History of prior penile prosthesis or artificial urinary sphincter surgery
- 16. Revision penile prosthesis surgery

Study Feasibility: At Mayo Clinic – Rochester, we perform approximately 200 penile prosthesis procedures per year amongst the three prosthetic surgeons, of which an estimated 90% are primary prosthesis placements. The majority of patients who are candidates for penile prosthesis placement will meet our inclusion criteria. Given that we will be comparing administration of two local anesthetics that are generally considered as standard of care, and the fact that our study protocol involves minimal additional time commitment on the part of the patient participants, we anticipate a high rate of patient willingness to participate in the trial. We anticipate study dropout to approach approximately 20%. Therefore, we estimate the study duration inclusive of patient accrual, data collection, and statistical analysis to be approximately 24 months.

Biospecimens

Not-applicable

Review of medical records, images, specimens

Check all that apply (data includes medical records, images, specimens).

Only data that exists before the IRB submission date will be collected.

Date Range for Specimens and/or Review of Medical Records:

Examples: 01/01/1999 through 12/31/2015, or all records through mm/dd/yyyy.

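### The 130 planned patients do not leave the 110 needed for 90% power: about 106 to 107 remain at the stated 18% dropout and 104 at 20%

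*Combined protocol and SAP*

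**What the plan says.** The Power Statement, under Data Analysis, sets the base size: "A total sample size of 110 (55 per arm) provides 90% power to detect a clinically relevant difference". The inputs are a "difference in discharge prescription opioids of 37.5 OME", "assuming a common standard deviation of 60 OME", and a "two-sample, two-sided, equal-variance t-test with significance alpha level 0.05". It then moves from 110 to the enrolment target: "With an anticipated drop-out rate of 18%, total sample size will be 130 (65 per arm").

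Target accrual, under Subject Information, repeats the total, "130 patients (65 patients in each treatment arm"), and tells the reader that "this accounts for the necessary statistical power plus an anticipated approximately 20% dropout rate". Study Feasibility uses the same rounded rate: "We anticipate study dropout to approach approximately 20" percent.

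The document prints no inflation formula. It does not define dropout, and it provides neither for replacing patients who are lost nor for imputing their outcomes.

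**The concern.** If 110 patients with outcome data are needed and a fraction d of those enrolled is lost, the enrolment target is 110/(1 − d). At 18% that is 134, not 130. The figure of 130 is what results from adding 18% to 110, which treats dropout as a share of the patients who remain rather than of those enrolled.

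At stake is the accuracy of the sample-size justification. The plan tells the ethics board that 130 preserves the required power after dropout. Any later report that repeats the statement would claim 90% power under a dropout assumption that does not give it.

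**Working it through.** **Inputs, all from the document.** Difference 37.5 OME, common SD 60 OME, two-sided alpha 0.05, equal-variance t-test, 110 patients for 90% power, 130 enrolled 1:1, dropout 18% (Power Statement); dropout approximately 20% (Target accrual, Study Feasibility).

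**Step 1: reproduce the base size.** Power comes from the noncentral t distribution with n₁ + n₂ − 2 degrees of freedom and noncentrality 37.5 / [60 × √(1/n₁ + 1/n₂)].

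- 55 per arm: noncentrality 37.5 / (60 × √(2/55)) = 37.5 / 11.44 = 3.28; power 0.901.
- 54 per arm: power 0.896.

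So 110 reproduces. It is also the smallest equal-arm total that reaches 90%, so it has no slack to absorb a shortfall.

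**Step 2: patients left from 130.**

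- 18% dropout: 130 × 0.82 = 106.6, that is 106 to 107, or 3 to 4 short of 110.
- 20% dropout: 130 × 0.80 = 104, or 6 short.
- Largest dropout that still leaves 110: (130 − 110)/130 = 20/130 = 15.4%. As a check, 130 × 0.85 = 110.5.

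**Step 3: power with those numbers.**

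| Situation | Patients per arm | Power for 37.5 OME | Difference detectable with 90% power (OME) |
|---|---|---|---|
| As planned | 55 / 55 | 90.1% | 37.4 |
| 18% dropout, 107 left | 54 / 53 | 89.3% | 38.0 |
| 18% dropout, 106 left | 53 / 53 | 89.0% | 38.1 |
| 20% dropout, 104 left | 52 / 52 | 88.4% | 38.5 |

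**Step 4: the total that would match.**

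- 18%: 110/0.82 = 134.1, so 135, or 136 with equal arms.
- 20%: 110/0.80 = 137.5, so 138 (69 per arm).

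**Step 5: where 130 may come from.** 110 × 1.18 = 129.8, which rounds to 130; equivalently, 20/110 = 18.2%. Both treat the 20 extra patients as a share of 110. This is an inference, since no formula is printed, and the shortfall in steps 2 and 3 does not depend on it. The same method at 20% would give 110 × 1.20 = 132.

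**The case against.** The strongest objection is that the loss is too small to matter. It is 0.8 to 1.1 points at 18% dropout and 1.7 points at 20%. With all 110 patients kept, a true SD of about 61.1 or 61.7 OME instead of 60 would cost as much as having 53 or 52 per arm. An SD of 59.0 or 58.4 would bring those reduced arms back to 90%. The document gives no source for the SD of 60, so the error lies within the uncertainty of the calculation's own inputs. This stands, and it is why the remedy is a corrected statement and not a larger trial. It does not make the statement correct.

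Second, dropout is undefined, and a patient who leaves early may still supply some data: the primary endpoint includes daily use, and follow-up occurs on days 3, 7 and 14. That is a fair limit on precision, since the figures of 106 to 107 and 104 are complete-case counts. But the endpoint also includes total consumption, the medication log runs to day 14, and the plan describes no analysis of partial records. It therefore gives no basis for counting such patients in full.

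Third, the plan may have meant 18% as a margin on top of 110. That would explain the number, but it is not the usual meaning of a dropout rate, and the document attaches the rate to target accrual and to study dropout.

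Finally, approximately 20% is compatible with 18%. The two figures are not treated here as a contradiction.

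**Conclusion.** The point holds. The base calculation is sound; only the step from 110 to 130 is wrong. At 18% dropout the trial keeps 106 to 107 patients and about 89% power. At 20% it keeps 104 and about 88%. The stated 90% requires dropout of no more than 15.4%, which is lower than any rate in the document.

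The effect is minor: 1 to 2 points of power, or a detectable difference of about 38.0 to 38.5 OME in place of the planned 37.5.

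The conclusion assumes that dropout is a share of enrolled patients, that a dropout contributes no primary outcome, and that losses fall about equally on the two arms.

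**What to change.** Keep 130 and correct the Power Statement, for example: 130 randomized patients (65 per arm) give about 89% power at 18% dropout and about 88% at 20%; 90% power is retained if dropout is 15% or less. Say that these figures count only patients with primary outcome data. Give the same dropout rate under Target accrual, Study Feasibility and the Power Statement, for consistency, and amend the Target accrual remark so that it no longer says 130 covers both the power requirement and the dropout.

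This costs wording only: enrolment, data collection and conduct are unchanged, and the stated power becomes 1 to 2 points less favourable. Only if 90% at the stated dropout must be guaranteed does the total change, to 136 (six more patients) at 18% or 138 (eight more) at 20%.

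Adjustment for the baseline anxiety and catastrophizing scores could be prespecified separately to gain precision. It should not be counted on to restore 90%, because the document gives no correlation between those scores and opioid use.
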